Abbreviations: BP = blood pressure; C-SSRS = Columbia-suicide severity rating scale; CT = computed tomography; ECG = electrocardiogram; EQ-5D-5L = EuroQol - 5 Dimension - 5 Level; HbA1c = glycated hemoglobin; hsCRP = high-sensitivity C-reactive protein; IWQOL-Lite-CT = Impact of Weight on Quality of Life-Lite-Clinical trials version; MRI = magnetic resonance imaging; MRI-PDFF = magnetic resonance imaging - proton density fat fraction; NAFLD = non-alcoholic fatty liver disease; NASH = nonalcoholic steatohepatitis; OGTT = oral glucose tolerance test; PHQ-9 = Patient Health Questionnaire-9; PR = pulse rate; SF-36v2 = Short-Form 36-item Health Survey Version 2; TNFα = tumor necrosis factor-α; VAS = visual analog scale.

Protocol I8F-JE-GPHZ(b)

Table 3. Study Period III- Early Discontinuation and Follow-Up Period

Activity	Early Discontin	nuation and Follow-U	Comment			
Visit Number	99	ED	801	At ED visit, participants who are unable or unwilling to continue the study treatment for any reason will perform an ED visit. If the participant is discontinuing during an unscheduled visit or a scheduled visit, that visit should be performed as the ED visit. At Visit 801, for participants who discontinue or complete the study within 72 weeks, Visit 801 (safety follow-up visit) should be performed 4 weeks after the last visit during the 72-week treatment period.		
Weeks of treatment	72		4 weeks post end of treatment period			
Allowable duration (days)	±7		±7	The visit date after randomization visit is determined in relation to the date of the randomization visit (± the allowed visit window).		
Fasting visit	X	X	X	If the participant is not fasting, the participant should be called in for a new visit within the visit window.		
Adverse events and product complaints	X	X	X			
Hypoglycemic events	X	X	X			
Concomitant medications	X	X	X			
Lifestyle management counseling		X		Counselling on diet and exercise, to be performed by a dietician or equivalent qualified delegate, will include calculation of individualized energy requirement and methods to change dietary composition and amount of physical activity. The lifestyle management counseling may be delivered on a separate day from the rest of that visit's study procedures but must occur within the visit window.		
Review diet and exercise goals		X				
Participant returns study drugs and injection supplies		X				

Activity	Early Discontin	uation and Follow-U	Comment			

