Weight	X	Х	X	At Visit 99, participants wanting to discontinue the study before Week 72 will be asked to return for Visit 99 at 72 weeks ±7 days after randomization primarily for body weight measurement and assessment of adverse events. If the participant is unwilling to attend Visit 99, it should be documented in the participant medical record that the participant has refused to attend.

Activity	Early Discontinuation and Follow-Up Period		Comment	
Visit Number	99	ED	801	At ED visit, participants who are unable or unwilling to continue the study treatment for any reason will perform an ED visit. If the participant is discontinuing during an unscheduled visit or a scheduled visit, that visit should be performed as the ED visit. At Visit 801, for participants who discontinue or complete the study within 72 weeks, Visit 801 (safety follow-up visit) should be performed 4 weeks after the last visit during the 72-week treatment period.
Weeks of treatment	72		4 weeks post end of treatment period	
Allowable duration (days)	±7		±7	The visit date after randomization visit is determined in relation to the date of the randomization visit (± the allowed visit window).
Fasting visit	X	X	X	If the participant is not fasting, the participant should be called in for a new visit within the visit window.
Waist circumference	X	X	X	
Electrocardiogram		X	X	Single ECGs should be collected centrally at ED and Visit 801
Vital signs (sitting BP and PR)		X	X	Vital sign measurements should be taken before collection of blood samples for laboratory testing, at visits where required. The participant should sit quietly for 5 minutes before vital sign measurements are taken. For each parameter, 2 measurements will be taken using the same arm; the recordings should be taken at least 1 minute apart.
Clinical laboratory tests				
Hematology		X	X	
Clinical chemistry		X	X	
Other chemistry				
Cystatin-c		X	X	

Activity	Early Discontinuation and Follow-Up Period		Comment	
Visit Number	99	ED	801	At ED visit, participants who are unable or unwilling to continue the study treatment for any reason will perform an ED visit. If the participant is discontinuing during an unscheduled visit or a scheduled visit, that visit should be performed as the ED visit. At Visit 801, for participants who discontinue or complete the study within 72 weeks, Visit 801 (safety follow-up visit) should be performed 4 weeks after the last visit during the 72-week treatment period.

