8.9. Immunogenicity Assessments

At the visits and times specified in the Schedule of Activities (Section 1.3), venous blood samples will be collected to determine antibody production against tirzepatide.

To interpret immunogenicity results, a venous blood sample will be collected at the same time points to determine the blood concentration of tirzepatide. All samples for immunogenicity should be taken predose when applicable and possible. The actual date and time (24-hour clock time) of each sampling will be recorded. Immunogenicity will be assessed by a validated assay designed to detect ADAs in the presence of tirzepatide at a laboratory approved by the sponsor. Antibodies may be further characterized for cross-reactive binding to endogenous counterparts, and their ability to neutralize the activity of tirzepatide or endogenous counterparts. Sample collected at Visit 801 will assess immunogenicity at washout of tirzepatide (5 half-lives post end of treatment).

Treatment-emergent ADAs are defined in Section 9.4.5.

Long-term sample retention is defined in Section 10.1.11.

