Analysis Dataset	Analysis Type	Baseline	Postbaseline
SS	1.1) Treatment-Emergent Adverse Events	The baseline period is defined as the start of screening and ends prior to the first dose in of study treatment (typically at Week 0).	Starts after the first dose of study treatment and ends at the end of the study period (including off-drug follow up visit).
SS	1.2) Treatment-Emergent Abnormal Labs a , Vital Signs, and ECGs.	Baseline will include all scheduled and unscheduled measurements during the baseline period (Visit 1 to Visit 3)	Postbaseline will be defined as above (1.1). All scheduled and unscheduled measurements will be included.
SS	1.3) Change from Last Baseline to Week xx and to Last Postbaseline for Labs a ,Vital Signs, and ECGs.	The last scheduled and unscheduled non-missing assessment recorded during the baseline period defined above (1.2).	Postbaseline will be defined as above (1.1). Only scheduled visits will be included. The early discontinuation (ED) visits are considered scheduled visits.

Table GPHZ.4.1. Baseline and Postbaseline Definitions for Safety Analysis

Abbreviations: ECGs = electrocardiogram; SS = Safety Analysis Set.

For the primary and secondary efficacy endpoint analyses, data for participants with missing values at the 72-week visit will be imputed based on the method described in Section 4.3.2. Otherwise, missing values will not be explicitly imputed except for the parameters with only 1 postbaseline measure during the analysis period per schedule of activity, where last observation carried forward (LOCF) approach will be applied to impute the endpoint when ED measure is available.

End of study participation for a participant will be the earliest of date of death, date of withdrawal from further participation in the study, or date of safety follow-up visit (Visit 801). For participants considered to be lost-to-follow-up, end of study participation will be the date of lost-to-follow-up reported by the investigator. Participant data included in the database after the last date of study participation (including safety follow-up period) will be excluded from statistical analysis.

Statistical treatment comparisons will only be performed between tirzepatide 10 mg or 15 mg, and placebo. Since the trial is not adequately powered to detect difference among tirzepatide doses, comparisons among tirzepatide doses will not be performed unless otherwise specified.

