Abbreviations: ANCOVA = analysis of covariance; BL = baseline; BMI = body mass index; EWL = excess weight loss; MMRM = mixed model for repeated measures; SAT = subcutaneous adipose tissue; VAT = visceral adipose tissue.

Table GPHZ.4.4. Secondary and Exploratory Efficacy Measures for IGT, Hyperlipidemia, NAFLD and Other Parameters

Analysis variable	Criteria/Measures	Analysis set	Analysis method	Additional Information
Change in IGT related parameters (24, 52, and 72 weeks)	Mean change from BL in  Fasting glucose HbA1c Fasting insulin C-peptide HOMA2-%B HOMA2-%S Matsuda Index Insulin Secretion Beta-cell function	(1)Efficacy analysis set; (2) Efficacy analysis set - participants with IGT at BL; (3) Efficacy analysis set - participants with normoglycemic at BL	MMRM model in Section 4.3.2.1	
Change in hyperlipidemia related parameters (24, 52, and 72 weeks)	Mean change from BL in  TG TC VLDL-C LDL-C (direct) HDL-C Non-HDL-C FFA	(1) Efficacy analysis set - participants with hyperlipidemia at BL; (2) Efficacy analysis set	MMRM model in Section 4.3.2.1	
Change in NAFLD related parameters (24, 52, and 72 weeks)	Mean change from BL in  ALT  AST  GGT  AST/ALT ratio  K-18 (M30)  Pro C3  ELF  FIB-4 index	(1) Efficacy analysis set; (2) Efficacy analysis set - participants with NAFLD at BL	MMRM model in Section 4.3.2.1	

Analysis variable	Criteria/Measures	Analysis set	Analysis method	Additional Information
Change in blood pressure (24, 52, and 72 weeks)	Mean change from BL in     Systolic blood pressure     Diastolic blood pressure	Efficacy analysis set	MMRM model in Section 4.3.2.1	
Change in uric acid (24, 52, and 72 weeks)	Mean change from BL in  • Uric acid	Efficacy analysis set	MMRM model in Section 4.3.2.1	
Change in laboratory tests (24, 52, and 72 weeks)	Mean change from BL in  • Adiponectin (high molecular weight and total)  • Leptin  • hs-CRP  • TNFα  • eGFR  • Urinary albumin/creatinine ratio	Efficacy analysis set	MMRM model in Section 4.3.2.1	Exploratory objective
Time to onset of T2DM during 72 week treatment period	Onset of T2DM during 72 week treatment period from BL	Safety analysis set - participants with IGT at BL	Kaplan Meier plot will be used for estimation of survival rates over time Log-rank test will be used to compare survival curves	Exploratory objective To compare TZP 10 mg, 15mg and pooled TZP doses with placebo for participants with IGT at BL

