# 4.5. Safety Analyses

Unless specified otherwise, safety assessments will be based on the SS (Table GPHZ.3.1). All data collected between randomization and the end date of study participation will be included, regardless of the adherence to study drug.

The statistical assessment of homogeneity of the distribution of categorical safety responses, between tirzepatide doses and placebo, will be conducted using Fisher's exact test, unless specified otherwise.

The mean change from baseline differences among treatments at all scheduled visits will be assessed via an MMRM using REML. Unless specified otherwise, if the safety parameter is assessed at the 72 weeks, then the model will include treatment group, visit and treatment-by-visit interaction and stratification factors as fixed effects, and baseline value of the safety parameter as a covariate. To model the covariance structure within participants, the unstructured covariance matrix will be used. If this model fails to converge, the covariance structures specified in Section 4.3.2.1 will be tested in order until met convergence. If the data does not warrant the MMRM model, then ANCOVA model will be conducted.

For selected safety parameters, time-to-first-event analysis via the Cox-proportional hazards model may be conducted. Participants without the event will be censored at the end of study participation. For participants experiencing the event, the "time-to-first-event" will be the time (in weeks) from first dose to first occurrence of the event.

Where necessary, the rate of events will be analyzed using a generalized linear mixed-effects model, assuming the number of events follow a negative binomial distribution and with treatment as a fixed effect. The logarithm of days during the active treatment period will be adjusted as an offset, to account for possible unequal treatment duration of follow-up among participants.

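### SAP 4.1 can end participation at Visit 801, which excludes the Week 72 Visit 99 of some early leavers from the safety and treatment-regimen analyses

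*SAP*

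**What the plan says.** **Cut-off.** SAP 4.1 sets the end of participation at the "earliest of date of death, date of withdrawal from further participation in the study, or date of safety follow-up visit (Visit 801". Visit 99 is not in the list. It continues: "Participant data included in the database after the last date of study participation (including safety follow-up period) will be excluded from statistical analysis". SAP 4.5 uses the same end date to bound the safety data.

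**Visit dates.** In Protocol 1.3, Table 3, a participant who cannot or will not continue treatment has an ED visit, and the visit at which the person stops serves as that visit. Then: "Visit 801 (safety follow-up visit) should be performed 4 weeks after the last visit during the 72-week treatment period", with a ±7-day window. For people who want to leave early, the same table has this: "asked to return for Visit 99 at 72 weeks ±7 days after randomization primarily for body weight measurement and assessment of adverse events".

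**What Visit 99 records.** Adverse and hypoglycemic events, concomitant medication, C-SSRS, PHQ-9, the self-harm forms, weight and waist. It has no HbA1c and no clinical chemistry. The ED visit and Visit 801 have both.

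**Analysis sets.** SAP 3 defines the FAS and SS regardless of adherence to study drug. The EAS stops 7 days after the last dose (14 days for imaging). SAP 4.3.3.2 imputes missing Week 72 weight from same-arm participants who were measured after stopping drug.

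**Related dates.** For people lost to follow-up, "end of study participation will be the date of lost-to-follow-up reported by the investigator". For the optional Cox analyses of selected safety parameters, "Participants without the event will be censored at the end of study participation". The exploratory diabetes analysis is of "Onset of T2DM during 72 week treatment period from BL", by Kaplan-Meier and log-rank, with no censoring rule stated.

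**The concern.** A rule that takes the earliest of several dates works only if no planned visit can come after them. Here one can. An early leaver who has had Visit 801 is still asked back at Week 72. Read literally, the SAP then collects that visit and excludes it.

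The loss falls only on people who stopped early, which is the follow-up that an assessment irrespective of adherence exists to include. Two things are at stake: late off-drug safety information in the SS, and the off-drug Week 72 weights that feed the treatment-regimen imputation. With too few of those weights, SAP 4.3.3.2 switches to placebo-based imputation, so the cut could also change which imputation method is used.

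**Working it through.** The plan states no figure on this point, so there is none to reproduce. The check compares dates and then sizes the result.

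**1. Dates.** Let the ED visit fall at week *w*. From Table 3:
- Visit 801 = *w* + 4, with a window of *w* + 3 to *w* + 5.
- Visit 99 = 72, with a window of 71 to 73.
- Visit 801 comes first at nominal dates if *w* + 4 < 72, that is *w* < 68.
- It comes first at every point of both windows if *w* + 5 < 71, that is *w* < 66.
- Nominal gap from the cut to Visit 99 = 72 − (*w* + 4) = 68 − *w*.

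| ED week | Visit 801 | Gap to Visit 99 (weeks) |
|---|---|---|
| 24 | 28 | 44 |
| 36 | 40 | 32 |
| 52 | 56 | 16 |
| 64 | 68 | 4 |

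**2. Which date applies.** Protocol 7.2 says that people who agree to give endpoint information at the end are not counted as discontinued. For them there is no withdrawal date, so Visit 801 sets the cut. The same section also says that a participant leaving with an ED visit is permanently discontinued from the study at that time. If that date were taken as withdrawal, the cut would come earlier still and could remove Visit 801 too.

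**3. Which analyses are touched.**
- EAS (primary): no. Data more than 7 days after the last dose are already outside it.
- FAS (treatment-regimen): yes, through the Visit 99 weight.
- SS: yes, through adverse events, C-SSRS and PHQ-9.

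**4. How many.** SAP 5 assumes 25% dropout: 0.25 × 87 = 21.75, about 22 per arm, and 0.25 × 261 = 65.25, about 65 in total. This is a ceiling, because deaths, losses and refusals bring no Visit 99. The share that attends both Visit 801 and Visit 99 is not given. Assuming 20% to 80%: 22 × 0.2 = 4.4 and 22 × 0.8 = 17.6, so about 4 to 18 weights per arm (13 to 52 in total).

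**5. Lost-to-follow-up date.** Neither document says whether the reported date is the last contact or the day the loss was declared. To bound the effect, assume that a share *L* is lost at Week 36, that the reported date runs *e* weeks past last contact, and that everyone else is followed to Week 76. Inflation of follow-up = *L·e* / [(1 − *L*)·76 + *L*·36].
- *L* = 5%, *e* = 4: 0.2 / 74 = 0.27%.
- *L* = 25%, *e* = 12: 3 / 66 = 4.55%.

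**6. Diabetes onset.** With the end date at Visit 801, HbA1c and glucose are measured on that date. If the end date moves to Visit 99, up to 68 − *w* weeks have no scheduled glycemic test (44 weeks for ED at Week 24). For a completer, Visit 801 is near Week 76, past the 72-week window of the endpoint.

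**The case against.** The strongest reply is that Visit 801 is meant to follow Visit 99. Protocol 7.2 and the visit-window table in Appendix 14 both treat Visit 21 and Visit 99 as alternatives for the endpoint visit. Appendix 14 then names Visit 801 beside them, and Table 3 gives Visit 99 as Week 72 of treatment. On that reading nothing is excluded. The reading is available but not secure. Table 3 lists Visit 99 under early discontinuation and follow-up, not under the treatment period. Protocol 8.9 says: "Sample collected at Visit 801 will assess immunogenicity at washout of tirzepatide (5 half-lives post end of treatment", which fits a visit soon after treatment ends. At the least the order is undefined, and site practice would decide which data survive.

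A second reply also stands. Under Protocol 7.1, people who stop drug stay in the study for all planned measurements. Anyone who keeps the regular visits through Visit 21 has Visit 801 afterwards and loses nothing.

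A reader might infer more than the documents support:
- *Lost participants are censored too late.* Protocol 7.3 describes when someone counts as lost, not which date is entered. The date is undefined, not shown to be late. The exposure summary in SAP 4.5.1 uses the last study visit, so only optional time-to-event analyses would be touched.
- *Unobserved time counts as diabetes-free.* The SAP does not tie diabetes onset to the end-of-participation date. The gap is a missing censoring rule.
- *A Visit 801 held after Week 72 is not a washout sample.* For someone months off drug it is still past 5 half-lives. Only the timing differs.
- *All 65 assumed dropouts lose many months of data.* What is lost is one visit per person who returns.

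**Conclusion.** The point holds in limited form. On the path ED visit, Visit 801, Visit 99, with ED before about Week 66 to 68, the SAP 4.1 wording excludes Visit 99. That conflicts with analysis sets defined regardless of adherence and with the imputation in SAP 4.3.3.2.

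The primary efficacy result does not depend on it. The size rests on two assumptions: the plan's 25% dropout as a ceiling, and a 20% to 80% return rate that is ours. Together they put about 4 to 18 Week 72 weights per arm at stake, with the safety assessments made at the same visits. The undefined lost-to-follow-up date and the missing diabetes censoring rule are gaps to close alongside, not demonstrated errors. The change should be made because a stated rule, followed literally, discards collected data.

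**What to change.** 1. **SAP 4.1.** Define end of participation as the date of death or of withdrawal of consent to further contact; otherwise the latest attended visit among Visits 21, 99 and 801. Say that Visit 99 data belong to both FAS and SS. This needs saying for the FAS because it is limited to the treatment period and Table 3 lists Visit 99 elsewhere.
2. **Protocol Table 3, 7.2, 8.3.1 and Appendix 14.** Reconcile the order of Visits 99 and 801 for people who stop early, and when adverse event collection ends. Section 8.3.1 now ends it at the follow-up visit, although Visit 99 also assesses adverse events.
3. **Lost to follow-up.** Define the date, for example as last contact.
4. **Time to diabetes.** Censor at the last glycemic assessment up to the Week 72 visit. This must accompany item 1, because Visit 99 has no HbA1c or glucose and the later end date would otherwise add time without glycemic testing.

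The cost is wording in the SAP and a protocol clarification, with no new visits or tests. The diabetes analysis has slightly less person-time.

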### 4.2. Participant Dispositions

Reasons for screen failure as reported by investigators will be summarized.

Frequency counts and percentages of all participants screened, randomized, and receiving at least 1 dose of study drug will be summarized by treatment group, if applicable.

Of the randomized population, frequency counts and percentages of participants who completed the study, prematurely discontinued the study (and/or study drug), including reason for premature discontinuation, will be summarized by treatment group.

A Kaplan-Meier analysis of time from randomization to premature discontinuation from study and/or study treatment by treatment group will be provided. A time-to-event analysis of premature study treatment discontinuation will also be conducted.

#### 4.3. Primary Endpoints Analysis

The assessment of efficacy objectives will be guided by the "efficacy" estimand using the EAS.

#### 4.3.1. Definition of endpoints

The primary efficacy measure will be percent change in body weight AND percentage of participants who achieve ≥5% body weight reduction from randomization at 72 weeks. The percent change in body weight at each nominal visit is defined as:

(postbaseline body weight [kg] – baseline body weight [kg]) / baseline body weight [kg] \* 100.

Both percent change in body weight and percentage of participants who achieve ≥5% body weight reduction will be summarized by treatment and nominal visit (week) from randomization to 72 weeks.

#### 4.3.2. Main analytical approach

The analysis related to efficacy estimand will be conducted utilizing data in the EAS.

#### 4.3.2.1. Main Analytical Approach for Continuous Measures

For the mean percent change in body weight from randomization, a MMRM will be conducted. Restricted maximum likelihood (REML) will be used to obtain model parameter estimates and the Kenward-Roger option will be used to estimate the denominator degrees of freedom. The response variable of MMRM will be the percent change in body weight from baseline values, obtained at each scheduled post-baseline visit.

For MMRM, the independent variables of analysis model are treatment group, visit, and treatment-by-visit interaction, stratification factors: baseline IGT (yes or no); baseline hyperlipidemia (based on TG; yes or no); baseline NAFLD (yes or no) and sex (female, male) as fixed effects, and baseline body weight as a covariate. An unstructured covariance structure will model relationship of within-patient errors. If this model fails to converge, the following variance covariance structures will be tested in order until convergence is achieved:

- heterogeneous Toeplitz
- heterogeneous first order autoregressive
- heterogeneous compound symmetry

- Toeplitz
- first order autoregressive
- compound symmetry

The first covariance structure that converges will be used.

With the aid of the MMRM analysis, 2-sided 95% CI for mean percent change in body weight from randomization to the 72-week visit for tirzepatide 10 mg or 15 mg QW, compared to placebo, will be derived and summarized. The resulting least squares mean (LSM) estimates of mean percent change in body weight from baseline will be plotted by visit and by study treatment.

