## 2. Statistical Hypotheses

The alternative hypotheses for the primary objective are the following:

- H10: QW tirzepatide 10 mg is superior to placebo for percent change in body weight from randomization AND percentage of participants who achieve ≥5% body weight reduction at 72 weeks.
- H15: QW tirzepatide 15 mg is superior to placebo for percent change in body weight from randomization AND percentage of participants who achieve ≥5% body weight reduction at 72 weeks.

The above 2 hypotheses will be tested in parallel, each at a 2-sided significance level of 0.025.

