#### 2.1. Multiplicity Adjustment

The type 1 error will be controlled in the strong sense at a two-sided significance level of 0.05 because two hypotheses ( $H_{10}$  and  $H_{15}$ ) will be tested in parallel each at a 2-sided significance level of 0.025. Since superiority of each one of two hypotheses will be declared if and only if both statistical tests (regarding percent change in body weight and percentage of participants who achieve  $\geq$ 5% body weight reduction) are significant, no multiplicity adjustment is planned for these 2 tests.

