# 4.6.3. Subgroup analyses

# 4.6.3.1. Subgroup Analysis of Efficacy Endpoints

Efficacy subgroup analyses will be guided by the efficacy estimand in EAS. Subgroup analyses by the following baseline characteristics will be provided:

- age ( $<65, \ge 65 \text{ years}$ )
- sex (female and male)
- baseline BMI (<35,  $\ge35$  kg/m^2)
- baseline BMI ( $\ge 27$  and < 30,  $\ge 30$  and < 35,  $\ge 35$  and < 40,  $\ge 40$  kg/ m^2)
- glycemic status at screening (normoglycemia versus IGT)
- hyperlipidemia status at screening (TG;  $\geq$ 150 and <150 mg/dL)
- NAFLD status at screening (HFF; ≥5% and <5%), analysis population will be the mITT excluding subjects with missing HFF measure at screening

For the reporting in the CSR, the outcome measures for the subgroup analyses will include:

- Percent change in body weight from randomization at 72 weeks.
- Proportion of participants achieving at least 5% body weight reduction from randomization to 72 weeks.

For the other purpose (eg. the publication), the outcome measures for the subgroup analyses will include:

- Proportion of participants achieving at least 10%, 15% and 20% body weight reduction from randomization to 72 weeks.
- Change in waist circumference (cm) from randomization to 72 weeks.
- Change in VAT area (cm^2), SAT area (cm^2) and VAT/SAT ratio from randomization to 72 weeks.
- Change in HFF (%) from randomization to 72 weeks.
- Change in Short-Form-36 Health Survey version 2 from randomization to 72 weeks.
- Change in IWQOL-Lite-CT Physical Function score from randomization to 72 weeks.

For the percentage change in body weight from randomization at 72 weeks, for each subgroup analyses aforementioned, the following analyses will be conducted:

• Conduct MMRM model on the subgroup only with terms of treatment group, visit, treatment-by-visit-interaction and stratification factors as fixed effects, and baseline body weight as a covariate. Variance-covariance structure for within-patient errors will be same as Section 4.3.2.1.

• Full MMRM model: treatment group, visit, subgroup, treatment-by-visit-interaction, treatment-by-subgroup-interaction, subgroup-by-visit-interaction, treatment-visit-subgroup-interaction, and stratification factors as fixed effects, and baseline body weight as a covariate. Variance-covariance structure for within-patient errors will be same as Section 4.3.2.1.

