# 5. Sample Size Determination

Approximately, 348 participants will be screened to achieve 261 randomly assigned to study intervention (approximately 87 participants per intervention group).

The sample size determination assumes that evaluation of superiority of tirzepatide 10 mg and tirzepatide 15 mg to placebo will be conducted in parallel, each at a 2-sided significance level of 0.025 using a 2-sample t-test. Additionally, a difference of at least 11% mean body weight percentage reduction from randomization at 72 weeks for tirzepatide 10 mg and/or tirzepatide 15 mg compared with placebo, a common SD of 10%, and a dropout rate of 25% are assumed for statistical power calculations. Under the assumptions above, randomizing 261 participants in a 1:1:1 ratio to tirzepatide 10 mg, tirzepatide 15 mg, and placebo provides more than 90% power to demonstrate superiority of each tirzepatide dose to placebo.

The chosen sample size and randomization ratio also provides >90% power to establish superiority of tirzepatide 10-mg and/or tirzepatide 15-mg doses to placebo in terms of proportion of participants achieving at least 5% body weight reduction at 72 weeks, conducted in parallel using a Fisher's exact test, each at a 2-sided significance level of 0.025, assuming 25% of placebo-treated participants and 90% of tirzepatide-treated participants achieve the goal and a dropout rate of 25%.

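### If the unstructured MMRM fails to converge, the SAP falls back to structured covariances with model-based standard errors, so the confidence intervals and single-endpoint p-values can be miscalibrated; a sandwich variance would prevent this.

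*SAP*

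**What the plan says.** SAP 4.3.2.1 analyses percent change in body weight by REML, with Kenward-Roger, an unstructured within-patient covariance and a treatment-by-visit term. If that model does not converge, the order is heterogeneous Toeplitz, heterogeneous AR(1), heterogeneous compound symmetry, Toeplitz, AR(1), compound symmetry. The selection rule is "The first covariance structure that converges will be used". There is no fit criterion, and no empirical variance is mentioned.

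The list is reused:

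- SAP 4.6.3.1, for both the within-subgroup and the full interaction MMRM: "Variance-covariance structure for within-patient errors will be same as Section 4.3.2.1".
- SAP 4.5: "If this model fails to converge, the covariance structures specified in Section 4.3.2.1 will be tested in order until met convergence". This section adds ANCOVA if the data do not warrant an MMRM.
- The tables in SAP 4.4.3 send the continuous repeated-measures endpoints to the same model.

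Protocol 9.4.3.1 names only the unstructured covariance, and SAP 4.9 does not list the fallback as a change.

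On error control, SAP 2 states: "The above 2 hypotheses will be tested in parallel, each at a 2-sided significance level of 0.025". SAP 2.1 adds that "superiority of each one of two hypotheses will be declared if and only if both statistical tests" are significant.

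**The concern.** A model-based standard error is right only if the fitted covariance is close to the true one. Kenward-Roger adjusts for estimating the covariance parameters in small samples; it takes the structure itself as given.

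Two features of this trial make the fallback structures doubtful.

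- **Equal variance.** Percent change is zero by construction at randomization, and the plan assumes an SD of 10% at Week 72. An SD that grows over the visits is therefore plausible. Toeplitz, AR(1) and compound symmetry force one variance on every visit, so Week 72 would be tested with roughly an average variance.
- **Visit spacing.** Heterogeneous Toeplitz and AR(1) give each visit its own variance but make correlation depend on visit order only. Weight is scheduled at Weeks 4, 8, 12, 16, 20, 24, 36, 48, 52, 60 and 72, with gaps of 4 to 12 weeks. A wrong correlation pattern also shifts the fitted Week 72 variance.

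At stake is whether an interval or p-value from a fallback fit means what it says.

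**Working it through.** **Inputs from the documents.** Alpha is 0.025 two-sided per dose (SAP 2). SAP 5 assumes "a difference of at least 11% mean body weight percentage reduction from randomization at 72 weeks" and "a common SD of 10%, and a dropout rate of 25% are assumed for statistical power calculations", with 261 randomized, so 87 per arm. The Schedule of Activities gives 11 post-baseline weights, so unstructured has 11 × 12 / 2 = 66 covariance parameters.

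**Inputs not in the documents.** SDs before Week 72 and between-visit correlations are assumed below. The probability of non-convergence is unknown.

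**The plan's own figure.** SAP 5 says that "randomizing 261 participants in a 1:1:1 ratio to tirzepatide 10 mg, tirzepatide 15 mg, and placebo provides more than 90% power". With 87 × 0.75 ≈ 65 per arm, the SE is 10 × √(2/65) = 1.754 and z = 11 / 1.754 = 6.27. Power at two-sided 0.025 is above 0.999, so the stated lower bound holds.

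**A case that can be done by hand.** Assume complete data, variance growing linearly with time, and a compound-symmetry fit.

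1. Compound symmetry uses the average variance over visits. The visit weeks sum to 352, so average / Week 72 variance = 352 / (11 × 72) = 352 / 792 = 0.444.
2. SE ratio = √0.444 = 0.667.
3. Type I error = 2 × [1 − Φ(2.241 × 0.667)] = 2 × [1 − Φ(1.494)] = 0.135, against 0.025.
4. Coverage of a nominal 95% CI = 2Φ(1.96 × 0.667) − 1 = 2Φ(1.307) − 1 = 0.81.

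**The range.** For each structure, the limiting REML fit was found under assumed true covariances: Week 4 SD of 2, 3, 5 or 10% reaching 10% at Week 72, several correlation shapes, and 25% monotone MCAR dropout. Type I error = 2 × [1 − Φ(2.241 × SE_model / SE_true)].

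| Structure | Week 72 type I error (nominal 0.025) |
|---|---|
| Heterogeneous Toeplitz | 0.009 to 0.066 |
| Heterogeneous AR(1) | 0.009 to 0.061 |
| Heterogeneous compound symmetry | 0.017 to 0.028 |
| Toeplitz, AR(1), compound symmetry; SD rising from 2-5% to 10% | 0.067 to 0.226 |
| The same three; SD flat at 10% | 0.021 to 0.035 |

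Heterogeneous Toeplitz and AR(1) are conservative when correlation depends on elapsed weeks. They are inflated when correlation rises over time.

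**Simulation check, and the sandwich.** True null, 87 per arm, SD 3% rising to 10%, correlation rising over time, 4,214 to 6,000 tests per structure:

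| Structure | Model-based SE | Sandwich SE |
|---|---|---|
| Heterogeneous Toeplitz | 0.048 | 0.026 |
| Heterogeneous compound symmetry | 0.024 | 0.025 |
| AR(1) | 0.128 | 0.026 |
| Compound symmetry | 0.149 | 0.023 |

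The other two structures were not simulated in this check. It omits baseline covariates and uses a t distribution with 190 df in place of exact Kenward-Roger df.

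**Both co-primary tests together.** Assume no effect on either endpoint, complete data, 87 per arm, Week 72 SD 10%, a common mean change of 0 to −5%, and an unadjusted Wald logistic test for 5% responders. With the model SE at 0.67 to 0.88 of the true SE, the weight-change test alone rejects in about 0.05 to 0.14. Both tests reject together in about 0.011 to 0.022.

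**The case against.** A reader might infer that any fallback makes the Week 72 test reject at several times its level, and so breaks the strong control claimed in SAP 2.1. The documents do not support that, for four reasons.

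- **The fallbacks differ.** The first three give Week 72 its own variance, and one of them is near nominal. The large rates need the last three, reached only after unstructured and all three heterogeneous models fail.
- **The rates are conditional.** They rest on SD paths and correlations that neither document gives. With a flat SD the problem nearly disappears.
- **A dose claim needs both tests.** If neither endpoint has an effect, the joint rejection rate cannot exceed that of the responder test. Inflation would reach H10 or H15 only if mean weight change were null while responder rates truly differed. One gap remains: SAP 4.3.2.2 fills missing Week 72 weights from the MMRM before dichotomizing, and the complete-data check does not cover this. Loss of control is therefore not shown, rather than excluded.
- **The primary decision would rarely change.** With 66 parameters and 261 participants, unstructured will probably converge. At the planned effect, even an SE overstated by 17% leaves z = 6.27 / 1.17 = 5.4.

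The subgroup and safety MMRMs, where failure is likelier, also carry no multiplicity claim. All of this stands. It narrows the point, but it does not make a miscalibrated interval correct where a fallback is used.

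**Conclusion.** The point holds as a calibration problem confined to fallback fits. Model-based standard errors are kept under structures chosen only because they converge. Under the assumptions above, the Week 72 weight-change test then has an error rate anywhere from about 0.01 to 0.066 for the heterogeneous structures, and about 0.07 to 0.23 for the equal-variance ones if the SD grows. Coverage of a nominal 95% CI is about 81% for compound symmetry if variance grows linearly with time.

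The likeliest places are analyses that combine many visits with few participants, such as the weight MMRM in participants aged 65 or over or with BMI of 40 or more, and the three-way interaction model. Endpoints measured only at Weeks 24, 52 and 72 need 3 × 4 / 2 = 6 covariance parameters and are much less exposed. The per-dose error control in SAP 2.1 is not shown to fail.

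**What to change.** Add to SAP 4.3.2.1, so that it carries into 4.4.3, 4.5 and 4.6.3.1:

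*If a structure other than unstructured is used, standard errors, CIs and p-values will use the empirical (sandwich) estimator with a small-sample correction and a compatible degrees-of-freedom method, in place of Kenward-Roger.*

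Optionally, remove the three equal-variance structures. Alternatively, keep them as a last resort with the sandwich variance, so that a rule remains if the heterogeneous models also fail.

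The cost is a sentence or two of SAP text and a program option, settled before unblinding. Nothing changes if unstructured converges. There are two limits. Sandwich standard errors are noisier in very small subgroups, hence the correction. They also do not remove bias in the Week 72 estimate when the covariance is wrong and dropout is missing at random, which is a further reason to put the equal-variance structures last or drop them.
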